9.7.3 Handling of the missing data

No imputation will be allowed in the retrospective study to reflect the real-world data.

9.8 QUALITY CONTROL

Before the study launch, participating physicians will be trained on the protocol and study conduct procedures by Boehringer Ingelheim (or designee).

In keeping with the non-interventional design employed in this study, site interaction (e.g., direct contact between site study staff or patients) is minimized if needed.

During the study, the occurrence of any protocol violations will be determined. After these actions have been completed and the clinical database has been declared to be complete and accurate, it will be locked. Quality control will be conducted to ensure data accuracy, completeness, and reliability. All information will be kept confidential.

Boehringer Ingelheim or designated personnel will assure database quality processes are followed including the review of the data entered into the CRFs by investigational staffs for completeness and accuracy, and in accordance with the data validation plan.

9.9 LIMITATIONS OF THE RESEARCH METHODS

Data collection

A retrospective study is a suitable design to obtain instantly enormous information on the use of medications and their outcomes under the clinical practice. However, data integrity may be limited by data availability in the medical chart. The lack of data of interest may be one of the limitations. Considering the characteristics of COPD, the data regarding relevant assessments (CAT, mMRC, or spirometry) and medications for COPD are common tools to manage the disease progression. Sponsor, designated personnel, and sites will do their best to collect the available data of interest.

Unbalanced patients' characteristics

This study is a non-randomized retrospective study, which means the characteristics of enrolled patients may be imbalanced and influential to study endpoints. Hence, this study plans to apply propensity score matching for the study cohorts to balance the baseline characteristics. Significant difference between patients using different regimens is easier to be observed after the baseline matching.

Patient pool

The sample size of COPD patients using tiotropium/olodaterol (Spiolto[®]) may be less because this product is late on the market in Taiwan on April 18, 2016. To screen more possible patients, the entry criteria are non-restrictive and will permit data collection from a broad patient population.

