9.2.2 Study population

The data will be retrospectively abstracted from the medical chart after eligibility assessment. Eligible patients will be categorized into the cohort A (patients treated with Tio + Olo), B (patients treated with other LABA/LAMA therapy), and C (patients treated with LAMA therapy).

Inclusion criteria

Patients who fulfil **ALL** the following criteria are included.

1. Patients who diagnosed with COPD who were prescribed with LABA/LAMA (FDC or free combo) as a new initiation or switching from other therapy (i.e., single/dual/triple), or newly receiving LAMA treatment for 3 months at least prior to 30 June 2018
2. Male or female patients ≥ 40 years of age

Exclusion criteria

Patients who meet the following criterion are not included.

1. Patients with documented diagnosis of bronchial asthma, asthma-COPD overlap syndrome (ACOS), bronchiectasis, cystic fibrosis, or lung cancer

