9.2.3 Study visits

The abstracted data will be recorded on the case report form (CRF). **Table 1** shows the collected data at different retrospective period of the medical chart.

Table 1 Data collection schedule

| Variables | Time points | Eligibility assessment | Data collection retrospectively | | |
|----------------------------------|-------------|------------------------|---------------------------------|-------------------------|--------------------------------------|
| | | | Before the index date | Index date [#] | 1-year follow-up period [†] |
| Eligibility assessments | X | | | | |
| Demographics ¹ | | | | X* | |
| Diagnosis of COPD ² | | | | X* | |
| Smoking status ³ | | | | X* | |
| Comorbidity ^{4, §} | | X [◊] | X | X | |
| COPD assessments [‡] | | | | | |
| CAT ⁵ | | X ^Δ | X | X | |
| mMRC ⁶ | | X ^Δ | X | X | |
| Examinations [‡] | | | | | |
| Spirometry data ⁷ | | X ^Δ | X | X | |
| Eosinophils | | X ^Δ | X | X | |
| Records [‡] | | | | | |
| Acute exacerbations ⁸ | | X ^{&} | X | X | |
| Hospital admissions ⁹ | | X ^{&} | X | X | |
| Treatments | | | | | |

| Variables | Time points | Eligibility assessment | Data collection retrospectively | | |
|--|-------------|------------------------|---------------------------------|-------------------------|--------------------------------------|
| | | | Before the index date | Index date [#] | 1-year follow-up period [†] |
| Related to COPD ^{10, \$} | | | X ^{11, ♦} | X | X |
| Related to comorbidities ^{12, \$} | | | X [◊] | X | X |
| Rescue treatments ^{13, ‡} | | | X [◊] | X | X |
| Oxygen therapy ^{14, \$} | | | X [◊] | X | X |
| Others ^{15, \$} | | | X [◊] | X | X |

[#]Not later than 30 June 2018; defined as the date of COPD patients in the cohort A and B starting using LABA/LAMA therapy regardless of new initiation or switching from other single/dual/triple treatment, or the date of the patients in the cohort C starting using LAMA treatment

[†]Not later than 1 year after the index date

^{*}The data nearest to the index date will be collected.

[◊]The data 6 months before the index date will be documented.

^{\$}The data will be collected every 6 months (allowed window: ± 1 month).

[‡]All available data on the medical chart will be recorded.

[△]The data nearest to the index date will be collected as the **Baseline**.

[&]The data/events ever since patients started receiving LABA/LAMA or LAMA therapy will be collected (maximum: trace back to 1 year before the index date).

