9.3.3 Covariates

9.3.3.1 Eligibility assessments

The eligibility should be checked by investigators before the data collection (see **Section 9.2.2** in detail). The following assessments are conducted to determine the eligibility for each patient:

1. Review the medical chart to confirm if a subject with COPD were prescribed with LABA/LAMA or LAMA therapy for 3 months at least (not later than 30 June 2018). Additionally, a subject must be ≥ 40 years of age.
2. Check the medical chart to exclude the patient with bronchial asthma, ACOS, bronchiectasis, cystic fibrosis, or lung cancer

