9.5 STUDY SIZE

Based on the projected market share and per physician's clinical experience, data from approximately 1,800 patients will be collected.

Among these patients, using Tio + Olo FDC versus other LABA/LAMA therapy (FDC or free combo) is assumed the ratio of 1:2 (~ 300 Tio + Olo, ~ 800 other LABA/LAMA therapy). If we assume the same annualized event rates as in the Taiwanese subgroup analysis report of DYNAGITO¹ (i.e. 0.78 per patient-year for Tio + Olo and 0.90 per patient-year for other

therapies), expecting the 95% CI for incidence rate ratio to be 0.87 (0.768, 0.978), with good precision. The following **Table 2** also shows that with smaller sample size, the precision is reduced (wider 95% CI).

Table 2 Sample size estimation

| Tio + Olo | | Other | | Incidence rate ratio (95% CI) |
|---------------------|-------------|---------------------|-------------|-------------------------------|
| True Incidence rate | Sample size | True Incidence rate | Sample size | |
| 0.78 | 300 | 0.90 | 800 | 0.87 (0.768, 0.978) |
| 0.78 | 300 | 0.90 | 300 | 0.87 (0.751, 1.000) |
| 0.90 | 300 | 0.97 | 800 | 0.93 (0.829, 1.039) |
| 0.90 | 300 | 0.97 | 300 | 0.93 (0.810, 1.062) |
| 0.90 | 200 | 0.97 | 200 | 0.93 (0.786, 1.094) |
| 0.90 | 200 | 0.97 | 100 | 0.93 (0.734, 1.173) |

In this table, it is assumed that all patients have on average ~ 2 patient-year exposure.

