9.7.1 Main analysis

The propensity score matching approach* will be used to balance the baseline characteristics between the study cohorts. These data will be compared descriptively between patients receiving different regimens (Tio + Olo vs. other LABA/LAMA vs. LAMA). If the propensity score matching is done, the difference before and after matching will be considered both.

For the primary outcome

Time to the first moderate or severe COPD exacerbation will be compared between different cohorts using Kaplan-Meier curves with the incidence and time to events, and statistical significance will be assessed using log-rank tests.

Time to first acute exacerbation starts from the index date to the date of the first acute exacerbation recorded on the CRF. Patients with exacerbation free at the time of escalating to ICS or no documented with exacerbations will be censored.

For secondary outcomes

- Time to escalating to dual/triple therapy will also be analysed using Kaplan-Meier curves and log-rank tests.
- The annualized rate of exacerbation with various severity will be calculated for each study group (episodes/patient-year), and the differences between the three cohorts will be compared by rate ratio.
- Results of lung function (i.e., spirometry data) and COPD assessments (i.e., CAT and mMRC) will be evaluated by the change from baseline. Pair *t*-test or other applicable statistical methods will be used for assessing the intra-group difference under a significance level of 0.05.
- Chi-square test or Fisher's exact test will be applied for categorical variables such as reasons for switching/escalating therapies, frequency, and percentage, etc.

*NOTE: Variables may include but not limited to age, gender, disease duration before index date, smoking status, body mass index, COPD assessment score (e.g., CAT and mMRC), spirometry data (e.g., FEV₁), oxygen therapy, comorbidities, disease severity, previous exacerbation, previous treatments, or eosinophil counts, where appropriate.

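### The index date has a latest limit but no earliest one, so cohorts B and C may include patients who started before Tio + Olo was available, leaving the cohort comparisons at risk of calendar-time confounding

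*Combined protocol and SAP*

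**What the plan says.** The index-date footnote to Table 1 (Section 9.2.3) reads "Not later than 30 June 2018; defined as the date of COPD patients in the cohort A and B starting using LABA/LAMA therapy". Inclusion criterion 1 (Section 9.2.2) asks for treatment "for 3 months at least prior to 30 June 2018", and for the LAMA cohort for patients "newly receiving LAMA treatment for 3 months at least prior to 30 June 2018". The eligibility check in Section 9.3.3.1 repeats the same upper date. None of these places, nor the abstract, gives an earliest index date.

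Section 9.9 (Patient pool) says of Spiolto that "this product is late on the market in Taiwan on April 18, 2016". It treats this as a threat to the size of cohort A and answers that "the entry criteria are non-restrictive and will permit data collection from a broad patient population". Section 9.5 sizes the study on "using Tio + Olo FDC versus other LABA/LAMA therapy (FDC or free combo) is assumed the ratio of 1:2", so cohort A is the marketed fixed-dose product, while cohort B takes other fixed-dose products and free combinations. Cohort C is newly started LAMA.

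For balancing the cohorts, the note in Section 9.7.1 begins "Variables may include but not limited to age, gender, disease duration before index date, smoking status, body mass index" and goes on to clinical variables. No index year or period is named. The Kaplan-Meier, log-rank and rate-ratio comparisons in that section carry no stated adjustment for, or stratification by, calendar time.

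**The concern.** The launch date gives cohort A a natural start to its accrual window. Cohorts B and C have no such start. A comparator patient indexed before 18 April 2016 had no chance of receiving Tio + Olo, so for that patient the comparison has no counterpart in cohort A (a failure of positivity).

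If prescribing practice, the readiness to add ICS (which censors the primary outcome and is itself part of a secondary outcome), or the completeness of charts changed over the years, that change would enter the contrast of cohort A with B or C and look like a treatment difference. The propensity score, as listed, is not aimed at this. The plan noticed the late launch but considered it only as a matter of sample size.

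**Working it through.** **Step 1. The index windows, side by side.**

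| Cohort | Earliest index date | Latest index date | Source |
|---|---|---|---|
| A (Tio + Olo) | 18 April 2016, by availability | 30 June 2018 | 9.9; 9.2.3 |
| B (other LABA/LAMA) | none stated | 30 June 2018 | 9.2.2; 9.2.3; 9.3.3.1 |
| C (LAMA) | none stated | 30 June 2018 | 9.2.2; 9.2.3; 9.3.3.1 |

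From 18 April 2016 to 30 June 2018 is 803 days, or 803 / 30.4375 = 26.4 months. If three months of therapy must be complete by 30 June 2018, the last usable start is about the end of March 2018 and the window is about 23.4 months.

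**Step 2. What a calendar effect could do to a rate ratio.** The plan gives no figure for this: neither the share of comparators indexed before launch nor any trend over time. Both are therefore assumptions. Let f be the share of comparators indexed before launch and m the recorded exacerbation rate in that period relative to the later one. With no true difference and no matching,

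apparent ratio = 1 / (1 + f(m − 1)).

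| f | m | Denominator | Apparent ratio (true value 1.00) |
|---|---|---|---|
| 0.5 | 1.1 | 1.05 | 0.95 |
| 0.5 | 1.2 | 1.10 | 0.91 |
| 0.5 | 1.3 | 1.15 | 0.87 |
| 0.5 | 0.9 | 0.95 | 1.05 |
| 0.5 | 0.8 | 0.90 | 1.11 |
| 0.5 | 0.7 | 0.85 | 1.18 |
| 0.2 | 1.1 | 1.02 | 0.98 |

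A second set of assumptions gives a similar range in one direction. Suppose rates fall by 2% or 5% a year and 20% to 60% of comparators were indexed on average 2 or 4 years before the rest. The ratio is then 1 / [(1 − f) + f(1 − d)^(−L)], with d the annual fall and L the lag in years. It runs from 0.99 (f = 0.2, d = 0.02, L = 2) to 0.88 (f = 0.6, d = 0.05, L = 4). A rising trend would push the other way.

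For scale, the ratio assumed in Section 9.5 for A against other LABA/LAMA is 0.78 / 0.90 = 0.87.

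**Step 3. What a common window would cost in precision.** For A against B, SE of the log rate ratio = sqrt[1/(0.78 × 300 × t) + 1/(0.90 × n_B × t)], with t the patient-years per patient, and 95% CI = 0.867 × exp(±1.96 SE). The first row of Table 2, 0.87 (0.768, 0.978), is reproduced at t = 1.5; at the stated exposure of about 2 the formula gives 0.781 to 0.962. I use t = 1 because follow-up is capped at one year.

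| Share of the 800 in cohort B kept (assumed) | n_B | 95% CI |
|---|---|---|
| 100% | 800 | 0.748 to 1.004 |
| 80% | 640 | 0.744 to 1.009 |
| 60% | 480 | 0.739 to 1.016 |
| 40% | 320 | 0.729 to 1.030 |

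The loss is small because cohort A, with 300 patients, contributes most of the variance: at full size 1/234 = 0.0043, against 1/720 = 0.0014 for B.

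**The case against.** Several points on the other side stand.

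- **No bias is shown.** A reader might infer that the comparison is confounded in favour of Tio + Olo. The documents do not support that. They give no distribution of index dates, do not show that any comparator started before April 2016, and report no trend. Poorer recording in older charts would lower the recorded rates and work against Tio + Olo.
- **The two ICD versions prove nothing here.** A reader might take the acceptance of ICD-9 codes as a sign that pre-launch patients are intended, or that coding differs between cohorts. Exacerbations are traced back one year before index, hence to April 2015 for the earliest cohort A patient, and the date of COPD diagnosis may be much older. Codes of both kinds could be needed even with a common window, and the plan does not say when coding changed.
- **Matching may help.** The candidate variables include previous exacerbations and previous treatments. Prior-year exacerbations are recorded under the same definition as the outcome, so matching on them could absorb part of a shift over time.
- **Calendar time is not ruled out.** The propensity list is expressly open-ended, and the contents list shows a redacted entry between 9.7.1 and 9.7.3 that could hold a related analysis.
- **The aims are modest.** The primary objective is to understand the occurrence of exacerbations, and Section 9.7.1 speaks of descriptive comparison.

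These points limit the claim but do not remove it. An open list commits no one to adding index period. Matching is itself conditional in Section 9.7.1, and unmatched results are to be considered as well, so early comparators would remain in those. Clinical matching cannot give a pre-launch patient any chance of having received the product. Whatever the redacted entry holds, the visible eligibility text has no lower limit. Log-rank tests between cohorts are planned, so the comparison will be read as one.

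**Conclusion.** The point holds as a design risk. As written, the plan admits comparators from a period in which Tio + Olo was unavailable, names no calendar variable, and so leaves the comparisons of A with B and C open to calendar-time confounding that clinical matching may reduce but cannot fully remove.

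Size and direction are unknown. Under the assumed inputs above, a true rate ratio of 1.00 could appear anywhere from 0.87 to 1.18, and as 0.98 in the mild case. Only the most extreme downward scenario with half of the comparators indexed early matches the 0.87 of Section 9.5. That 0.87 is a precision assumption for a rate ratio of A against other LABA/LAMA. It is not a target for the primary outcome, which is time to first moderate or severe exacerbation, and it was not set for cohort C. The illustration is for unmatched rates.

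The conclusion also assumes that cohort A means the fixed-dose product, as the abstract and Section 9.5 indicate; the cohort definition in Section 9.2.2 says only Tio + Olo.

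**What to change.** Restrict the comparative analyses of all three cohorts to index dates from 18 April 2016 to 30 June 2018. This can be written into inclusion criterion 1 and the index-date footnote of Table 1. The protocol version is dated 25 November 2019 and data collection was due to end on 30 November 2019, so the practical route is to define the comparative analysis population in Section 9.7 from the recorded index dates, with no new abstraction.

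Add calendar half-year of index to the propensity score variables as a firm commitment. The common window spans five half-years, the first one partial. Report the unrestricted comparison as a sensitivity analysis, with the number of patients per cohort indexed before launch, so that readers can see how much the restriction matters. Patients with earlier index dates can stay in the descriptive summaries.

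The cost is the loss of some B and C patients from the comparison and fewer potential matches for cohort A, which works against the broad pool that Section 9.9 chose. The effect on precision is slight: if 60% of cohort B remain, the expected interval for A against B at one patient-year goes from 0.748–1.004 to 0.739–1.016, before any further loss from matching.

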9.10 OTHER ASPECTS

No other aspect of the research method is not covered in the previous sections.

9.10.1 Data quality assurance

A quality assurance audit/inspection of this study may be conducted by the sponsor or sponsor's designees or by Institutional Review Board (IRBs)/Independent Ethics Committee (IECs) or by regulatory authorities. The quality assurance auditor will have access to all medical records and the investigator's study-related files and correspondence of this study.

9.10.2 Study records

Case Report Forms (CRFs) for individual patients will be provided by the sponsor.

- The principal investigator will sign and date the indicated places on the CRFs. These signatures will indicate that the principal investigator inspected or reviewed the data on the CRF, the data queries, and the site notifications, and agrees with the content.

9.10.2.1 Source documents

Source documents are original documents, data, and records from which the subject's CRF data are obtained from the medical chart mainly.

Source documents provide evidence for the existence of the patient and substantiate the integrity of the data collected. Source documents are filed at the investigator's site.

Data reported on the CRFs that are transcribed from source documents must be consistent with the source documents or the discrepancies must be explained. The investigator may need to request previous medical records or transfer records, depending on the study; also current medical records must be available.

For CRFs, the following data need to be derived from source documents:

- Patient identification (gender, date of birth, etc.)
- Patient participation in the study (substance, study number, patient number)
- Comorbidity
- Pharmacological and non-pharmacological history (prescription date, reasons, etc.)
- Hospitalization records (start/discharge date, etc.)
- Acute exacerbation records
- COPD assessments (CAT, mMRC, etc.)

The investigator should maintain a list of appropriately qualified persons to whom he/she has delegated trial duties. All persons authorized to make entries and/or corrections on the CRFs will be included on the Authority Form.

No information in source documents about the identity of the patients will be disclosed. No study document should be destroyed without prior written agreement between Boehringer Ingelheim and the investigator. Should the investigator wish to assign the study records to another party or move them to another location, he/she must notify Boehringer Ingelheim in advance.

9.10.2.2 Direct access to source data and documents

The investigator/institution will permit study-related monitoring, audits, IRB/IEC review and regulatory inspection, providing direct access to all related source data/documents. CRFs and all source documents, including progress notes and copies of laboratory and medical test results must be available at all times for review by the sponsor's clinical study monitor, auditor and inspection by health authorities (e.g., US Food and Drug Administration [FDA]). The auditor may review all CRFs. The accuracy of the data will be verified by reviewing the documents described in the **Section 9.10.2.1**.

10. PROTECTION OF HUMAN SUBJECTS

The study will be carried out in compliance with the protocol, the principles laid down in the Declaration of Helsinki, in accordance with the ICH Harmonized Tripartite Guideline for Good Clinical Practice (GCP), Good Epidemiological Practice (GEP), Guidelines for Good Pharmacoepidemiology Practice (GPP), and relevant BI Standard Operating Procedures (SOPs).

The investigator should inform the sponsor immediately of any urgent safety measures taken to protect the study subjects against any immediate hazard, and also of any serious breaches of the protocol/ICH GCP.

The rights of the investigator and of the sponsor with regard to publication of the results of this study are described in the investigator contract. As a general rule, no study results should be published prior to finalization of the study report.

10.1 STUDY APPROVAL, PATIENT INFORMATION, AND INFORMED CONSENT

This study will be initiated only after all required legal documentation has been reviewed and approved by the respective Institutional Review Board (IRB)/Independent Ethics Committee (IEC) and Competent Authority (CA) according to national and international regulations. The same applies for the implementation of changes introduced by amendments.

Prior to the start of data collection in the study, written informed consent must be obtained from each patient (or the patient's legally accepted representative) if requested by IRBs or the local regulatory organization. Each signature must be personally dated by each signatory and the informed consent and any additional patient-information form retained by the investigator as part of the study records. A signed copy of the informed consent and any additional patient information must be given to each patient or the patient's legally accepted representative.

The patient must be informed that his/her personal study-related data will be used by Boehringer Ingelheim in accordance with the local data protection law. The level of disclosure must also be explained to the patient.

The patient must be informed that his/her medical records may be examined by Quality Medicine auditors appointed by Boehringer Ingelheim, by appropriate IRB IEC members, and by inspectors from regulatory authorities.

